4.1 Inclusion criteria

Subjects who meet all of the following criteria are eligible to participate in this study:

1. Histologically-verified, previously untreated superficial or nodular BCCs on the scalp, face, extremities or trunk
2. >18 years of age at baseline
3. Legally competent, able to give verbal and written informed consent
4. Subject in good general health, is willing to participate and can comply with protocol requirements.
5. Fitzpatrick skin phototype I-III
6. Female subjects of childbearing potential¹ must be confirmed not pregnant by a negative urine pregnancy test prior to trial treatment.

¹Female subjects are considered of childbearing potential unless they have been hysterectomized or have undergone tubal ligation or have been post-menopausal for at least one year prior to first visit.

4.2 Exclusion criteria

Subjects meeting any of the following criteria are not eligible to participate in this study:

1. High-risk BCC
 - i. Tumors in the following anatomical locations: midface, orbital, ears
 - ii. Size: >20 mm in facial/scalp areas or > 50 mm in non-facial/non-scalp areas
 - iii. Subtype: morpheaform and micronodular BCC
 - iv. History: Gorlin syndrome or immunosuppression
2. Previous treatment of the BCC lesion
3. Known allergy to cisplatin or Efudix®
4. Other skin diseases present in the treatment area
5. Tattoo in the treatment area which may interfere with or confound evaluation of the study
6. History of keloids which is deemed clinically relevant in the opinion of the investigator
7. Fitzpatrick skin phototype IV-VI
8. Lactating or pregnant women

4.3 Restrictions during Trial

Patients must not receive concurrent treatment of the tumor/treatment area during the study.

Concomitant treatment for conditions other than the BCC may be continued throughout the trial without change in dosage.

4.4 Withdrawal Criteria

Subjects may withdraw from the trial for any of the following reasons:

1. Unacceptable treatment efficacy: the investigator is free to withdraw the subject at any time based on a medical judgment.
2. Unacceptable adverse events: any adverse event that the investigator or the subject considers unacceptable.
3. Exclusion criteria: any exclusion criteria which emerge/become apparent during the subject's participation in the clinical trial.
4. Voluntary withdrawal: subjects are free to withdraw from the clinical trial at any time and for any reason. If applicable, the subject's legal representative can withdraw the subject from the trial.

Subjects who discontinue treatment for any reason will be offered conventional BCC treatment and subsequent control according to national guidelines. Those who withdraw will be substituted. The research team will use already collected data after withdrawal unless the participant objects.

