6.1 Primary Outcome

Tolerability measured as:

I) Local Skin Reactions (LSRs)

Non-blinded, clinical evaluation of erythema, edema, flaking, crusting/scabbing and pustulation in treated areas will be performed by a physician using a FDA-approved 0-4 point LSR scale at Days 1, 5, 14 and 30 after AFL exposure (Appendix 1). Standardized,

clinical photographs are taken to document LSRs at each visit.

II) Side Effects

Non-blinded, clinical evaluation of prolonged erythema or edema, hyper- or hypopigmentation, scarring and infection will be evaluated up to 3 months after initial AFL treatment.

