7.4 Punch Biopsy and Blood Sampling

Prior to 4 mm biopsy local analgesic will be used to reduce pain. The biopsy may leave a punctiform scar. Needle-pricks associated with injection and blood sampling (preliminary study) are associated with discomfort. The risk of infection is low (<1%), and will be managed with antibiotics provided by the investigator.

8. Safety Considerations

Patients are followed closely in the initial 30 days after treatment and particularly in the first 14 days. Complete tumor removal is ensured through histological analysis at Month 3. In the event of inadequate treatment response at 3 months, or in the event of withdrawal, patients will receive conventional BCC treatment and follow-up according to national guidelines.

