8.2 Documenting and Reporting Adverse Events (AE) and Adverse Reactions (AR)

The investigators are responsible for routine assessments of AEs and ARs. All clinical complaints, symptoms, or signs that meet AE or AR definitions will be documented in the study record and the patient's medical record. Erythema and/or edema are anticipated sequelae of treatment; LSRs included in the LSR Grading Scale are reported as LSRs and not as AEs in the CRF, even if they require treatment. All AEs and ARs are described according to duration (start and end date), severity, association with drugs, whether further treatment is required and whether the AE has led to a serious adverse event. The location of the event is recorded as either "treated area" or "non-treated area". AEs and ARs will be followed until they have resolved.

The severity of an AE/AR is graded as:

- Mild: AE is transient and does not affect daily activities
- Moderate: AE causes patient discomfort and affect daily activities
- Severe: AE affect the patient's daily activities to a significant degree and may mean invalidity/incapacity for work or else be life-threatening.

The outcome of an AE/AR is described as:

- Resolved
- Improvement without sequelae
- Improvement with sequelae
- Persistent, follow-up necessary
- Persistent, follow-up not necessary

The investigators assessment of whether an AE is associated with the trial medication is classified as follows:

- Yes: an AE which after careful evaluation has a temporal association with the treatment and is in all probability related to the trial medication.
- No: an AE which after careful evaluation is definitely judged to be attributable to an external cause (disease, environmental exposure etc.) treatment and is in all probability related to the trial medication.

8.3 Documenting and Reporting of Serious Adverse Events (SAE) and Unexpected Serious Adverse Reactions (SUSAR)

The investigator is responsible for reporting all SAEs after the patient has signed the consent form until the final control visit. SAEs are reported within 24 hours to sponsor-investigator [name]

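### Section 4.4 does not separate stopping treatment from leaving the trial, so LSR duration and late side effects are likely to be cut short in patients who stop for intolerance

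*Combined protocol and SAP*

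**What the plan says.** Section 4.4 (Withdrawal Criteria) lists reasons for withdrawing from the trial. One concerns tolerability: "Unacceptable adverse events: any adverse event that the investigator or the subject considers unacceptable". The section then gives the consequences, moving between discontinuing treatment and withdrawing as if they were one event:

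- On care after stopping: "Subjects who discontinue treatment for any reason will be offered conventional BCC treatment and subsequent control according to national guidelines"
- On replacement, now speaking of withdrawal instead of discontinuation: "Those who withdraw will be substituted"
- On the data that remain available for analysis: "The research team will use already collected data after withdrawal unless the participant objects"

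Section 8 (Safety Considerations) repeats that "in the event of withdrawal, patients will receive conventional BCC treatment and follow-up according to national guidelines". Section 4.3 bars concurrent treatment of the tumor or treatment area during the study.

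The primary outcome (Section 6.1) is tolerability in two parts. LSRs are scored on a "0-4 point LSR scale at Days 1, 5, 14 and 30 after AFL exposure". Side effects, including "hyper- or hypopigmentation, scarring and infection will be evaluated up to 3 months after initial AFL treatment", form the second part. Section 3.4 makes both severity and duration of LSRs part of the outcome.

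Section 8.2 states that "AEs and ARs will be followed until they have resolved". The same section records reactions on the LSR scale as LSRs and not as adverse events. Section 9.2 defines the ITT population as all treated patients, with last observation carried forward (LOCF) for missing data, and the per-protocol population as patients who completed all control visits.

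**The concern.** In a tolerability trial, the patients who stop because of a reaction carry much of the information. Here the listed reasons for leaving include the outcome itself, so any loss of follow-up is related to what is being measured. How long the reaction lasted, and whether it left a scar or pigment change, can only be learned at Day 14, Day 30 and Month 3. If a patient stops in the first week and is no longer assessed, those answers are missing for that patient. No choice of analysis set restores them.

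This is separate from the question of substitution. Counting every treated patient in the denominator does not supply assessments that were not made.

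**Working it through.** **Do assessments continue after stopping?** The documents give no dropout rate or precision target, and Section 9.1 states that no formal calculation was done. There is therefore no planned figure to reproduce beyond 12 + 12 = 24. The question is first one of text.

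1. Section 4.4 offers discontinuers conventional treatment and control under national guidelines. It mentions no trial visit.
2. Section 4.3 bars other treatment of the site during the study. A patient who accepts the offer therefore no longer meets the conditions for taking part.
3. Those who withdraw are substituted, and Section 4.4 speaks only of using data already collected.
4. No section says that the Day 14, Day 30 or Month 3 assessments continue. None says that they stop.

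Together these imply that assessment ends, although no sentence states it.

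**What is already in hand when a patient stops?** Laser and cisplatin are given on Day 0. 5-FU is applied on Days 0, 1 and 5 and removed on Day 7. Apart from the optional repeat on Day 30, treatment can only be stopped in the first week, so the available LSR scores are those of Day 1 and perhaps Day 5. Section 7.2 expects erythema, then erosion, then healing, with local effects likely to resolve within 30 days. The healing part falls after the last available score.

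**What does LOCF put in the gap?**

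- LSRs: the Day 1 or Day 5 score is frozen to Day 30. A score taken before the peak understates severity. A score taken at the peak overstates duration.
- Scarring and pigment change: an absence noted in the first week is carried to Month 3.

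**Illustration.** Assumptions, not from the documents: k of 12 patients in one group stop after Day 5; all k later have sequelae that go unrecorded; none of the others has any. The exact (Clopper-Pearson) upper 95% limit for 0 of n is 1 − 0.025^(1/n). For n = 12 it is 1 − 0.025^(1/12) = 26.5%, and for n = 10 it is 1 − 0.025^(1/10) = 30.8%.

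| k | True rate (exact 95% CI) | ITT with LOCF | Completers only (upper limit) |
|---|---|---|---|
| 1 | 1/12 = 8.3% (0.2-38.5%) | 0/12 (26.5%) | 0/11 (28.5%) |
| 2 | 2/12 = 16.7% (2.1-48.4%) | 0/12 (26.5%) | 0/10 (30.8%) |
| 3 | 3/12 = 25.0% (5.5-57.2%) | 0/12 (26.5%) | 0/9 (33.6%) |
| 4 | 4/12 = 33.3% (9.9-65.1%) | 0/12 (26.5%) | 0/8 (36.9%) |

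If the two patients in the k = 2 row are substituted, 12 + 2 = 14 are treated. The true rate is then 2/14 = 14.3% (1.8-42.8%), while LOCF reports 0/14 and completers show 0/12. The pattern is the same.

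**How likely is at least one such patient?** With an assumed withdrawal probability p, the chance of one or more among 24 is 1 − (1 − p)^24. This gives 70.8% for p = 5%, 92.0% for p = 10% and 99.5% for p = 20%.

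**The case against.** The strongest case against is that the plan does not say visits end. It offers conventional care, and an offer of care does not exclude trial assessments. Scores up to discontinuation are kept and enter the all-treated set. Scarring and pigment change are not items on the LSR scale, so once recorded as adverse events or reactions they are followed to resolution, with no exception for patients who withdraw. The course is short, so a patient who stops after Day 5 already has two LSR scores. Section 7.2 reports that redness and edema after laser plus cisplatin peaked at 48 hours, so part of the peak may have been seen. A severe Day 5 score carried forward would not hide intolerance. Once other treatment of the site begins, later site data are confounded in any case.

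Much of this stands, and it limits the point. A reader might infer that the primary outcome is simply not observed in patients who stop, or that the protocol orders visits to cease. The documents support neither. A reader might also take the completers' 0/10 as what the trial would report, but that is a per-protocol figure; the all-treated set would show 0/12.

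The gap remains after these limits. Follow-up to resolution applies to events that meet the adverse event or reaction definitions and have been recorded. It does not clearly reach graded LSRs, and it schedules no visit at which a scar or pigment change that appears later would be found. The 48-hour peak is for laser plus cisplatin, not the combination under study, and it says nothing about duration or sequelae.

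**Conclusion.** The concern holds as a matter of truncation. As written, the plan implies that LSR and side-effect assessments end when a patient discontinues, and LOCF cannot repair the resulting loss of LSR duration and late side effects. The conclusion rests on reading Sections 4.3, 4.4 and 8 together, not on an express statement.

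The size cannot be known, because no expected withdrawal rate is given. In the illustration with two patients, a true sequelae rate of 16.7% in one group is reported as 0%. That is a worst case: both patients must have sequelae, and neither must be recorded through adverse event follow-up. For LSR scores the error can go in either direction, depending on when the patient stopped. The change is worth making because it is cheap and bears on the primary objective; the gap does not invalidate the trial.

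**What to change.** Amend Section 4.4 as follows:

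- Define discontinuation of treatment separately from withdrawal of consent.
- State that treated patients who stop remain on the LSR assessments already scheduled to Day 30 and the side-effect assessments to Month 3, unless they withdraw consent.
- Record the reason for stopping.
- If conventional treatment of the site starts, record an LSR assessment at that point where possible, and flag or censor later site data in the analysis. Add the matching sentence to Section 9.2.

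This concerns data collection only and leaves the choice and timing of conventional treatment as they are. The cost is protocol wording, since the visits already exist in the schedule, and a few extra attendances for patients who have stopped. The gain is limited once other treatment of the site has begun.

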9.1 Sample size

The primary objective of this explorative trial is to investigate tolerability of AFL-assisted cisplatin+5-FU to ensure that intolerable/severe or serious related adverse events remain minimal for the observed efficacy. While no formal statistical calculation has been performed, 12 superficial and 12 nodular BCCs in 24 subjects are considered sufficient to estimate benefit/risk of the treatment.

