9.2 Study populations

Treated study participants are divided into the following populations:

Per-protocol (PP) population:

Includes only patients that have completed all control visits as planned. Larger deviations such as

breach of inclusion criteria, inadequate outcome assessment or larger differences in treatment, are assessed before statistical analysis is conducted.

Intention-to-treat (ITT) population:

Includes all patients that have received treatment. In the event of missing data, the population is analyzed using the “last observation carried forward” approach to minimize bias associated with loss to follow up.

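### Every withdrawn patient is replaced and no analysis set is named as primary, so a completer analysis could look more favourable than the treated cohort

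*Combined protocol and SAP*

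**What the plan says.** Section 4.4 opens its list of withdrawal reasons with the two that coincide with the trial's outcomes. The first is "Unacceptable treatment efficacy: the investigator is free to withdraw the subject at any time based on a medical judgment". The second is "Unacceptable adverse events: any adverse event that the investigator or the subject considers unacceptable". It then states "Those who withdraw will be substituted", whatever the reason and whether or not the patient has been treated. The next sentence deals with data: "The research team will use already collected data after withdrawal unless the participant objects".

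Section 9.2 defines two populations. The PP set "Includes only patients that have completed all control visits as planned". The ITT set "Includes all patients that have received treatment", and for gaps it says: "In the event of missing data, the population is analyzed using the “last observation carried forward” approach to minimize bias associated with loss to follow". Neither 9.2 nor 9.3 assigns a population to the primary outcome (tolerability) or the secondary outcome (tumor size and clearance).

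On numbers, 9.1 says: "While no formal statistical calculation has been performed, 12 superficial and 12 nodular BCCs in 24 subjects are considered sufficient". Section 4 sets a ceiling of 12 per subtype. No section says whether a replacement counts within that ceiling or on top of it.

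**The concern.** In an uncontrolled, open-label tolerability trial, leaving because of a reaction is itself a tolerability result, and being withdrawn for poor efficacy is itself a treatment failure. If such patients are replaced and the results are then reported for those who finished, the reported cohort is selected towards people who tolerated the treatment and responded. There is no control arm to reveal this, and section 6 says the assessors are not blinded.

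A second route runs through the all-treated set. The skin-reaction scores run to Day 30 and the side-effect assessment to 3 months (6.1). A patient who leaves early has later values supplied by LOCF, and these may come from before the reaction peaked or before a late side effect could appear. What is at stake is the benefit/risk judgement that 9.1 expects the 24 patients to support.

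**Working it through.** **The plan's own figure.** 12 + 12 = 24, which agrees with 9.1. No error rate, expected rate or dropout allowance is given, so nothing further can be reproduced.

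**What happens to a treated patient who withdraws.**

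| Provision | Effect |
|---|---|
| 4.4, substitution | A new patient is added |
| 4.4, data | Values already collected are kept unless the patient objects |
| 9.2, ITT | The patient stays in; later values come from LOCF |
| 9.2, PP | The patient is out; a replacement who finishes is in |
| 4 and 9.1 | Silent on whether the replacement counts among the 12 |
| 9.2 and 9.3 | Silent on which set answers which objective |

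Substitution therefore adds patients and removes none from ITT. The two sets differ in exactly the patients with the poor outcomes.

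**Clearance.** The documents give neither a clearance rate nor a withdrawal rate, so both are assumed. Let p be true clearance and f the share of failures who are withdrawn and replaced until 24 complete.

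- Expected PP clearance = p / (1 − (1 − p)f).
- With p = 0.60 and f = 0.50: 0.60 / (1 − 0.40 × 0.50) = 0.60 / 0.80 = 75%.
- Number treated: 24 / 0.80 = 30, so 6 are withdrawn.
- Cleared: 0.75 × 24 = 18. All-treated clearance, with withdrawals counted as not cleared: 18/30 = 60%.
- Letting the number withdrawn vary at random (400,000 simulated trials) gives an all-treated mean of 60.5%.

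| True clearance | f | PP | All-treated (simulated) |
|---|---|---|---|
| 60% | 25% | 66.7% | 60.2% |
| 70% | 25% | 75.7% | 70.2% |
| 80% | 25% | 84.2% | 80.1% |
| 60% | 50% | 75.0% | 60.5% |
| 70% | 50% | 82.4% | 70.4% |
| 80% | 50% | 88.9% | 80.3% |

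Under the same replacement rule, the all-treated figure stays within about 0.5 points of the truth. The PP figure is 4 to 15 points too high.

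**In counts.** With 18 of 24 completers cleared (75.0%) and w replaced failures, all-treated clearance is 18/(24 + w): 18/26 = 69.2% for w = 2 and 18/28 = 64.3% for w = 4.

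**Intolerance.** With none of 24 completers intolerant and w withdrawals for intolerance, the all-treated rate is w/(24 + w): 2/26 = 7.7%, 3/27 = 11.1%, 4/28 = 14.3%. The completer rate is 0% throughout.

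**LOCF within ITT.** Section 7.2 reports that redness and edema after AFL with cisplatin peaked at 48 hours. Scoring is on Days 1, 5, 14 and 30.

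- A patient who leaves after Day 1 may have a pre-peak score carried forward, which understates severity.
- A patient who leaves at the peak has that score carried to Day 30, which overstates duration.
- Scarring, pigment change and prolonged erythema appear late, so an early absence carried to Month 3 favours the treatment.
- For clearance, a last assessment showing tumor carries forward as failure, but a Day 30 clearance carries forward as success at Month 3.

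**The case against.** A reader might infer that replacing patients in itself biases both results favourably. The documents do not support that. ITT keeps everyone treated, 4.4 retains collected data, and the calculation shows all-treated clearance almost unbiased under the same rule when withdrawals count as failures. The bias needs a further step: a completer analysis, a patient's objection to use of the data, or an unlucky LOCF value. The plan leaves all three open.

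The illustrative rates can also be challenged, and that stands. Section 3.3 offers a repeat treatment at Day 30 if tumor persists, and 6.2 places conventional treatment after the Month 3 finding of residual tumor. Nothing indicates that half of failures would be withdrawn. Likewise, a count of intolerant patients is not a planned endpoint; the primary outcome is reaction scores plus listed side effects, and scoring starts early enough that most who leave over a reaction will have contributed some scores.

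A reader might also infer that the worst reactions disappear from view after withdrawal. That goes too far: 8.2 requires adverse events and reactions to be followed to resolution, and 8.4 requires them in the final report. A narrower gap remains. Section 8.2 records reactions on the grading scale as skin reactions and not as adverse events, and nothing guarantees that they are scored after withdrawal.

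Finally, section 4 permits stopping short of 12 per group if, for example, all patients react severely. That works against filling the cohort with tolerators, but it also sits awkwardly with unrestricted replacement in 4.4. The two sections must be reconciled.

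**Conclusion.** The concern holds as a conditional risk. Replacement extends to treated patients who leave for reasons that are themselves outcomes, and the plan does not say whether completers or all treated patients answer each objective. If completers are used, the overstatement of clearance is about 4 to 15 points for assumed true clearance of 60% to 80% with a quarter to a half of failures withdrawn. Two to four withdrawals for intolerance would turn an apparent 0% into 7.7% to 14.3%. These sizes rest entirely on assumed rates. If all treated patients are used and withdrawals are counted as failures, the distortion in clearance is negligible. LOCF remains a weak point for tolerability, in a direction that cannot be fixed in advance.

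This should be fixed, with moderate confidence. The trial is exploratory and an all-treated set already exists, so the design is not undermined.

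**What to change.** In 4.4:

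- Limit substitution to patients who withdraw before the first AFL treatment, or state that replacements are additional and never displace a treated patient. If they are additional, say how this fits the ceiling in section 4.
- Separate stopping study treatment from leaving the study, so that willing patients keep the assessments already planned. This leaves the clinical decision to stop untouched.

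In 9.2:

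- Make the all-treated set primary for both tolerability and clearance, with PP supportive only.
- Instead of relying on LOCF, report withdrawal because of a reaction or adverse event as a tolerability outcome, and count withdrawal for inadequate efficacy as not cleared.
- Report every withdrawal with its reason, including any in which the patient objects to use of the data.

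The cost is protocol wording, with no visits beyond those planned. The downside is that fewer than 24 patients may complete and the reported rates may be less favourable. If replacements are declared additional, more than 24 may be treated.
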